6.3. Exploratory Objective

The exploratory objectives in the study include efficacy evaluation of baricitinib as assessed by:

- change from baseline at Weeks 16, 24 and 52 in structural joint damage as measured by modified Total Sharp Score (mTSS; van der Heijde 2000)
- proportion of patients with mTSS change ≤ 0 from baseline at Weeks 16, 24, and 52
- change from baseline to Weeks 16, 24, and 52 in joint space narrowing and bone erosion scores
- proportion of patients achieving DAS28-hsCRP ≤ 3.2 and DAS28-hsCRP < 2.6 at Weeks 12, 24, and 52
- proportion of patients achieving HAQ-DI improvement ≥ 0.22 and ≥ 0.3 at Weeks 12, 24, and 52
- proportion of patients achieving ACR20 at Week 24 and Week 52
- proportion of patients achieving ACR50 at Weeks 12, 24, and 52
- proportion of patients achieving 70% improvement in ACR criteria (ACR70) at Weeks 12, 24, and 52
- percentage change from baseline to Weeks 12, 24, and 52 in individual components of the ACR Core Set
- change from baseline through Week 52 in DAS28-hsCRP
- change from baseline through Week 52 in DAS28-erythrocyte sedimentation rate (ESR)

- proportion of patients achieving DAS28-ESR ≤ 3.2 and DAS28-ESR < 2.6 at Weeks 12, 24, and 52
- change from baseline to Week 24 and Week 52 in HAQ-DI score
- change from baseline to Weeks 12, 24, and 52 in CDAI score
- change from baseline to Weeks 12, 24, and 52 in SDAI score
- proportion of patients achieving a CDAI score ≤ 2.8 at Weeks 12, 24, and 52
- proportion of patients achieving an SDAI score ≤ 3.3 at 24, and Week 52
- proportion of patients achieving ACR/EULAR remission according to the Boolean-based definition at Weeks 12, 24, and 52
- proportion of patients achieving moderate and good EULAR responses based on the DAS28 at Weeks 12, 24, and 52
- evaluation of hybrid ACR (bounded) response at Weeks 12, 24 and 52
- change from baseline to Week 12, Week 24, and Week 52 in Functional Assessment of Chronic Illness Therapy Fatigue (FACIT-F) scale scores
- change from baseline to Weeks 12, 24 and 52 in European Quality of Life-5 Dimensions-5 Level (EQ-5D-5L) scores
- change from baseline to Weeks 12, 24 and 52 in Work Productivity and Activity Impairment-Rheumatoid Arthritis (WPAI-RA) scores
- evaluation of healthcare resource utilization through Week 52
- change from baseline to Weeks 12, 24 and 52 in duration of morning joint stiffness assessed at the visit using an electronic patient-reported outcomes (ePRO) tablet

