In addition to the LS means for each group, the within-group p-value, the standard deviation, minimum, median, and maximum will be displayed for continuous safety variables.

Data collected at early termination visits will be mapped to the next scheduled visit number for that patient.

The following is a description of the analysis groups planned for this study. Refer to Section 6.1.3 for the definitions of analysis populations used for the efficacy and safety analyses.

Analysis Groups for the Efficacy and Health Outcomes Data

Summaries of efficacy and health outcomes data for the Week 0 to Week 12 period, the Week 0 to Week 24 period with data up to rescue, and the Week 0 to Week 52 period with data up to rescue/switch will be presented according to the following treatment groups:

- Placebo: patients randomized to placebo excluding data obtained after the receipt of baricitinib 4 mg, either as rescue therapy or according to the protocol-designated switch to baricitinib 4 mg,
- Baricitinib 4 mg: patients randomized to baricitinib 4 mg excluding data obtained after the receipt of rescue therapy.

Summaries of efficacy and health outcomes data for patients who are rescued/switched will be presented according to the following treatment groups:

- Placebo (rescued): patients randomized to placebo who were rescued on or before Week 24,
- Placebo (switched, not rescued): patients switched to baricitinib from placebo at Week 24 and not rescued after the initiation of baricitinib,
- Placebo (switched, rescued): patients switched to baricitinib from placebo at Week 24 and rescued after initiation of baricitinib,
- Baricitinib (rescued): patients randomized to baricitinib who were rescued.

Analysis Groups for the Safety Data

Summaries of safety data for the Week 0 to Week 12 period and the Week 0 to Week 24 period with data up to rescue will be presented according to the following treatment groups:

- Baricitinib 4 mg: patients randomized to baricitinib excluding data obtained after the receipt of rescue therapy,
- Placebo: patients randomized to placebo using data obtained prior to the receipt of baricitinib as rescue therapy.

Summaries of safety data for the Week 0 to Week 52 period with data up to rescue/switch will be presented for baricitinib 4 mg for patients who were randomized to baricitinib excluding data obtained after receipt of rescue therapy.

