The change in health state index scores and EQ VAS score from baseline through Week 24 (Visit 11) may be analyzed using an ANCOVA model with the following terms: treatment, country/region, baseline joint erosion status, and baseline score. Within each treatment arm, the LS mean, SE of the LS mean, and p-value will be reported. The LS mean difference between baricitinib and placebo, 95% CI for the mean difference, and p-value will be reported. ANCOVA will be conducted after imputing the postbaseline missing values using mLOCF.

All the aforementioned health outcome analyses will be performed on the mITT population. Descriptive statistics will be provided for all the parameters by visit and treatment group for baseline and all postbaseline visits.

- **Healthcare Resource Utilization**

The healthcare resource utilization data will be collected by site staff regarding the number of visits to medical care providers such as general practitioners, specialists, physical or occupational therapists, and other non-physical care providers for services outside of the clinical study; emergency room admissions; hospital admissions; and concomitant medications related to the treatment of RA. These data will be collected to support economic evaluations of treatment. A summary table including the following will be presented for the period of the past 2 months prior to study treatment as baseline and summarized at baseline and at post-baseline intervals (Week 0 to Week 12, Week 0 to Week 24, Week 24 to Week 52, and Week 0 to Week 52).

Healthcare resource utilization – Healthcare providers:

A summary of the number of consultations of medical care providers for care/treatment of RA will be provided for the period of the past 2 months prior to the study treatment. It will also be summarized at the post-baseline intervals described earlier. The number of consultations will be totaled by days and patients for the categories:

- Healthcare Provider Consultation
- Emergency Room Consultation

The "Healthcare Provider Consultation" comprises the following:

- General Practitioner (Such as family doctor or primary care physician)
- Specialist

- Rheumatologist
- Occupational Therapist
- Physical therapist
- Non-physician care providers

For the “Emergency Room Consultation” every necessary Emergency Room (ER) or equivalent facility consultation will be counted.

Healthcare resource utilization – Inpatient Hospitalization:

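### Healthcare resource use is planned as totals without a time denominator, so with equal true use the Week 0-52 placebo total would be roughly half the baricitinib total

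*SAP*

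**What the plan says.** Protocol 6.3 lists as an exploratory objective the "evaluation of healthcare resource utilization through Week 52". Protocol 10.2 and SAP 6.16.1.1 say the data are collected to support economic evaluations.

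SAP 6.16.1.1 (Healthcare Resource Utilization) summarises a baseline of the 2 months before treatment and then "post-baseline intervals (Week 0 to Week 12, Week 0 to Week 24, Week 24 to Week 52, and Week 0 to Week 52". For provider and emergency room consultations, "The number of consultations will be totaled by days and patients for the categories". Hospitalisation is given as frequencies plus descriptive statistics for total days in hospital, and work status as a frequency table. No rate or patient-time denominator is given for any item.

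SAP 6.1 sets the general data cut for efficacy and health outcomes: "the Week 0 to Week 52 period with data up to rescue/switch will be presented according to the following treatment groups". Placebo is defined as "patients randomized to placebo excluding data obtained after the receipt of baricitinib 4 mg, either as rescue therapy" or through the planned switch. The other arm is "patients randomized to baricitinib 4 mg excluding data obtained after the receipt of rescue therapy". Under SAP 5.3.2 and 5.3.3, rescue starts at Week 16 in both arms, and every placebo patient still on placebo moves to baricitinib at Week 24.

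**The concern.** Consultations and hospital days accumulate with time, so a total means little without the time over which it was collected. Here that time differs between arms by design: a placebo patient's data stop at rescue or Week 24, while an unrescued baricitinib patient is followed to Week 52. The Week 0-52 totals would therefore differ between arms even if both used care at the same rate, and the placebo column for Weeks 24-52 would be essentially empty. The 2-month baseline has the same problem when set beside intervals of 12, 24, 28 and 52 weeks.

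A reader of the table could take a difference in follow-up for a difference in resource use, on an objective that is explicitly about use through Week 52. The SAP protects other outcomes from this. Adverse events get exposure-adjusted incidence rates (SAP 6.14.1). Week 0-52 safety data up to rescue/switch are shown for baricitinib only (SAP 6.1). Formal efficacy comparisons stop at Week 24 (SAP 6.11). Resource use has no corresponding rule for its totals.

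**Working it through.** The documents give no figure for resource use, observation time or rescue rate, so there is no plan figure to reproduce.

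**Inputs from the documents.** Earliest rescue is Week 16 in both arms and the placebo switch is at Week 24 (SAP 5.3.2, 5.3.3). Data are cut at rescue/switch (SAP 6.1). There are 144 patients per arm, and about 245 of 288 are planned to complete (Protocol synopsis).

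**Assumptions.** A share *r* is rescued, all at Week 16. The rate of use per week is constant and the same in both arms. There is no dropout unless stated. The ratio of totals then equals the ratio of mean weeks observed.

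**Weeks 0-52.**
- Placebo mean weeks = 16 + 8(1 − r)
- Baricitinib mean weeks = 16 + 36(1 − r)

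Equal rescue in both arms:

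| r | Placebo | Baricitinib | Ratio |
|---|---|---|---|
| 0% | 24.0 | 52.0 | 0.46 |
| 10% | 23.2 | 48.4 | 0.48 |
| 20% | 22.4 | 44.8 | 0.50 |
| 30% | 21.6 | 41.2 | 0.52 |
| 50% | 20.0 | 34.0 | 0.59 |

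Unequal rescue, 20-50% on placebo and 10-30% on baricitinib:
- lowest ratio (50% against 10%): 20.0/48.4 = 0.41
- highest ratio (20% against 30%): 22.4/41.2 = 0.54

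With constant-hazard dropout leaving 245/288 at Week 52, equal rescue gives 0.48 at 0%, 0.50 at 10%, 0.52 at 20% and 0.55 at 30%.

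**Weeks 0-24.** Both arms = 16 + 8(1 − r). At 30% placebo and 10% baricitinib rescue, 21.6/23.2 = 0.93.

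**Weeks 0-12.** This interval ends before rescue is possible, so rescue causes no imbalance.

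**Effect of a denominator.** Assume 2 consultations per patient-year in both arms, with no rescue or dropout:
- Placebo: 144 × 24/52.18 = 66.2 patient-years, total about 132.
- Baricitinib: 144 × 52/52.18 = 143.5 patient-years, total about 287.
- As rates, both arms are at 200 per 100 patient-years.

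**Baseline scale.** Two months is about 8.7 weeks. For patients observed throughout, unchanged use would appear as 12/8.7 = 1.4 times baseline over Weeks 0-12 and 24/8.7 = 2.8 times over Weeks 0-24.

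**If the SAP 6.1 cut were not applied.** An unrescued placebo patient would have 52 − 24 = 28 of 52 weeks on baricitinib, so the Week 0-52 totals would still not compare placebo with baricitinib.

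**The case against.** The strongest reply is that this is a descriptive table for one exploratory objective. No test, estimate or p-value is planned, and each interval and the baseline period are openly labelled. The Week 0-12 interval is already there, and SAP 6.1 already defines separate groups for rescued and switched patients. In the randomised period the distortion is small, and an empty placebo column for Weeks 24-52 would be seen as missing rather than as low use. All of this stands, and it limits the priority. None of it supplies a denominator or makes the Week 0-52 totals comparable.

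The consultation wording is loose, and the resource-use text does not restate the data cut, which comes from the general rule in SAP 6.1. That is a reason to clarify the text, not a defence of it.

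A reader might infer three stronger claims that the documents do not support:
- **Placebo must show less than half of baricitinib's use even if the drug does nothing.** Baricitinib data also stop at rescue, which costs 36 weeks per rescued patient against 8 on placebo. With no drug effect, rescue would be expected to be equal, and the ratio reaches one half at 20% rescue, or at about 10% with the planned dropout.
- **Use will appear six times baseline in both arms.** 52/8.7 = 6.0 applies only to patients observed for all 52 weeks, and no placebo patient is under this cut.
- **These totals are what an economic model will take in.** The documents give economic evaluation as the purpose of collecting the data, but describe no model and do not name these summaries as its input.

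**Conclusion.** The point holds for the missing denominator. Followed as written, the plan gives Week 0-52 totals that differ between arms when true use is equal, with placebo at roughly half of baricitinib: about 0.46-0.59 for equal Week 16 rescue of 0-50%, and about 0.41-0.54 for 20-50% placebo and 10-30% baricitinib rescue. These sizes rest on assumed rescue rates, all rescue at Week 16, a constant rate of use and no dropout. Later rescue at the investigator's discretion would shift them. Weeks 0-24 are mildly affected and Weeks 0-12 are not affected by rescue. Confidence is high on the missing denominator and lower on the exact ratio. Severity is modest because the output is exploratory and descriptive.

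**What to change.** In SAP 6.16.1.1:

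1. State that the rescue/switch data cut of SAP 6.1 applies to resource use.
2. Report provider consultations, emergency room visits, hospitalisations and hospital days as rates per patient-year, or per 2 months to match baseline, over time observed up to rescue/switch within each interval. Leave work status as a frequency table.
3. Base the baricitinib-placebo comparison on Week 0-12 and Week 0-24 rates.
4. Show Weeks 24-52 and 0-52 descriptively for baricitinib, with the rescued and switched groups of SAP 6.1 presented separately.

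The cost is SAP wording and one denominator per patient. No new data are needed: SAP 6.10 already derives duration of exposure up to rescue, and Protocol Attachment 1 schedules resource-use collection at Weeks 16 and 24. The Week 0-52 arm-against-arm column is lost, but it was not a valid comparison. A rate corrects for length of observation only. Patients who are rescued may differ in their use of care, so the Week 0-24 rates should carry that caveat.

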6.17. Interim Analysis and Data Monitoring

No data monitoring committee is planned for the study.

No interim analysis is planned. A blinded data review will occur when all patients have completed the double-blind treatment period (Part A) for the primary endpoint. Pooled primary endpoint, secondary endpoints, and safety measurements will be provided for study team review for the purpose of data cleaning and understanding. No decision related to sample size adjustment, efficacy, and inferiority will be made.

7. Unblinding Plan

There will be 2 planned database locks for this study: the first database lock will occur after all patients complete Part A (Week 24) and a final database lock at the end of the study. Only 1 unblinding will occur after the final database lock.

At the first database lock, by-visit data through Week 24 (Visit 11) will be locked but ongoing log-type entry forms for ongoing patients such as AEs and concomitant medications will remain unlocked. Blinded analyses will be conducted on the data that are collected through Week 24. X-ray results will only be analyzed after final database lock.

A final database lock is planned at the end of the study when all patients complete the study. The final analysis will include all data that are collected during the study. Sponsor, all investigators, study site personnel, and patients will remain blinded to treatment assignments until the final database lock.

8. References

[APA] American Psychiatric Association. Diagnostic and Statistical manual of Mental Disorders. 4th ed. DSM-IV. Washington, DC: American Psychiatric Association; 1994.

Brooks R. EuroQol: The current state of play. *Health Policy*. 1996;37(1):53–72.

Cancer Therapy Evaluation Program, Common Terminology Criteria for Adverse Events, Version 3.0, DCTD, NCI, NIH, DHHS, March 31, 2003.

Appendix 1. Algorithm for Determining ACR Response

Details presented in this appendix will use “x” as a generic symbol, and the appropriate number (either 20, 50, or 70) is to be filled in when implementing in dataset programming code.

ACRx response is defined as $\geq x\%$ improvement from baseline in tender joint count (68 joint counts), and $\geq x\%$ improvement in swollen joint count (66 joint counts), and $\geq x\%$ improvement in at least three of the following five items:

- Patient’s assessment of pain;
- Patient’s Global Assessment of Disease Activity;
- Physician’s Global Assessment of Disease Activity;
- HAQ-DI;
- hsCRP.

The following abbreviations will be used throughout this appendix to refer to the items needed in the algorithm definitions:

Parameter	Abbreviation for the Parameter
% improvement in tender joint count	TJC68
% improvement in swollen joint count	SJC66
% improvement in patient’s assessment pain	PATPAIN
% improvement in Patient’ Global Assessment of Disease Activity	PATGA
% improvement in Physician’s Global Assessment of Disease Activity	PHYGA
% improvement in HAQ-DI	HAQ
% improvement in hsCRP	hsCRP

For all seven parameters mentioned above, % improvement at a visit is calculated as:
(baseline value – value at visit) x 100 / baseline value.

To calculate the observed ACRx response at a visit:

- Step 1: If the patient discontinued from the study prior to reaching the visit, then STOP – assign ACRx response as blank (ie, missing). Otherwise, calculate the % improvement at the visit for all seven parameters as described above.
- Step 2:
 - o If TJC68 AND SJC66 are BOTH $\geq x\%$, then proceed to step3.
 - o If both are non-missing but one or both is $< x\%$, then STOP – assign the patient as a non-responder for ACRx.
 - o If either or both are missing, proceed as follows:
 - a. If both are missing, then STOP – assign ACRx response as blank (ie, missing).
 - b. If one of TJC68 or SJC66 is missing and the non-missing value is $< x\%$, then STOP – assign the patient as a non-responder for ACRx.

- c. If one of TJC68 or SJC66 is missing and the non-missing value is $\geq\chi\%$, then STOP
 - assign ACR χ response as blank (ie, missing).
- Step 3: Consider the following five variables: PATPAIN, PTGA, PHYGA, HAQ, and hsCRP.
 - o If three or more items are missing, then STOP – assign ACRx response as blank (ie, missing).
 - o If three or more items are non-missing, then proceed with the following order:
 - a. If at least three items are $\geq\chi\%$, then STOP – assign the patient as a responder for ACR χ .
 - b. If at least three items are $<\chi\%$, then STOP – assign the patient as a nonresponder for ACR χ .
 - c. If less than three items are $\geq\chi\%$, then STOP – assign ACR χ response as blank.

To calculate the ACRx response at post baseline visits up to Week 52 using NRI:

- Step 1: Calculate the % improvement at the visit for all seven parameters as described above.
- Step 2: If all seven parameters are missing at the visit, or if the patient discontinued from the study prior to reaching the visit, then STOP – assign the patient as a nonresponder for ACRx.
- Step 3: If at least one of the seven parameters is non-missing at the visit and the patient is still enrolled in the study, then use LOCF to fill in any missing values.
- Step 4: If TJC68 AND SJC66 are BOTH $\geq\chi\%$, then proceed to step 5. If both are nonmissing but one or both is $<\chi\%$, then STOP – assign the patient as a nonresponder for ACR χ . If either or both are missing, then STOP – assign the patient as a non-responder for ACR χ .
- Step 5: Consider the following five variables: PATPAIN, PATGA, PHYGA, HAQ, hsCRP.
 - o If three or more of the five items are non-missing, then:
 - If three or more of the five items are $\geq\chi\%$, then STOP – assign the patient as a responder for ACRx.
 - If less than three of those five items are $\geq\chi\%$, then STOP – assign the patient as a non-responder for ACRx.
 - o If three or more of the five items are missing, then STOP – assign the patient as a non-responder for ACRx.

